Endometrioid	32.30%	(80/248)		
Lung Adenocarcinoma	46.50%	(107/230)		
Lung Squamous	45.40%	(83/183)		
Ovary	14.30%	(65/456)		
Prostate	8.40%	(7/83)		
Stomach	53.60%	(81/151)		

STAT3 phosphorylation and suppressed the growth of human solid tumor xenografts with constitutive STAT3 activity. 10 Moreover, a strategy for patient selection is emerging. While activating mutations in JAK or STAT3 are not found in HNSCC, our recent comprehensive mutational profiling of HNSCC detected mutations in the PTPR family of genes in nearly one-third of tumors.27 Analysis of the 347 HNSCC tumors sequenced to date under the auspices of The Cancer Genome Atlas (TCGA) and our group. confirmed this high incidence of PTPR mutations (104/347, 30%). Further analysis demonstrated that

PTPR genes are mutated in a wide array of solid tumors sequenced to date under the auspices of the TCGA (see Table 1). Loss of function mutations in PTPRT and PTPRD lead to increased STAT3 phosphorylation, suggesting a tumor suppressor role. 30,31 Whole exome sequencing (n=374) and reverse-phase protein array data has been analyzed from 212 HNSCC tumors32. PTPR mutations were common and were associated with significantly increased phospho-STAT3 expression. Expression of PTPRT mutant proteins induced STAT3 phosphorylation and cell survival, consistent with an oncogenic "driver" phenotype. Computational modeling revealed functional consequences of PTPRT mutations on phosphor-tyrosine-substrate interactions. In addition to genomic aberrations, PTPRT is commonly methylated in HNSCC tumors (60%, 166/279 tumors analyzed to date in the TCGA); expression levels of PTPRT are significantly lower in these methylated tumors. Thus, silencing of key PTPR family genes may underlie STAT3 hyperactivation in HNSCC and other solid tumors. Identification and functional classification of these common genetic and epigenetic PTPR aberrations may permit companion biomarker development to select patients most likely to benefit from JAK inhibitors.

Phase 2 - Ruxolitinib Page 18 of 67

Figure 4: Decrease in pSTAT3_{Tyr705} expression with increase in concentration of Ruxolitinib

[figure not shown]

[figure not shown]
Figure 4. Cal 33 cells were treated with increasing concentrations of Ruxolitinib. After 24h, cells were harvested to obtain cell lysates. Forty micrograms of protein/lane were subjected to electrophoresis and immunoblotted for pSTAT3_{Tyr705} and total STAT3. B-tubulin was used as a loading control.

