Recognition that hyperactivated STAT3

likely results from increased signaling through upstream kinases, or loss of de-phosphorylation by silenced PTPRs, initially prompted investigation into the preclinical JAK1/2 inhibitor, AZD1480, in relevant HNSCC preclinical models. AZD1480 inhibited proliferation of eight HNSCC cell lines at low μ M concentrations (data not shown). Ruxolitinib is an ATP-competitive, oral, small molecule inhibitor of the JAK1 and JAK2 tyrosine kinases. Inhibition of wild type JAK1 and JAK2 respectively has an enzyme IC₅₀ of 3.3 (+/- 1.2) and 2.8 (+/- 1.2) nM.¹² Ruxolitinib blocked phosphorylation of pSTAT3 at Tyrosine 705 in dose-dependent fashion in the Cal33 HNSCC cell line (Figure 4). Furthermore, ruxolitinib inhibited growth of a FaDu HNSCC cell line xenograft, which harbors a loss-of-function *PTPRT* mutation, as compared to FaDu xenografts treated with vehicle control or ruxolitinib-treated PE/CA 34 HNSCC xenografts, which are wild type for *PTPRT* (Figure 4).

Phase 2 - Ruxolitinib Page 19 of 67

Figure 5: PTPRD or PTPRT mutations are found in 30% of HNSCC tumors. PTPRD and PTPRT mutations induce STAT3 activation, and increase sensitivity to JAK 1/2 inhibition.

The PTPRT/D mutations found in HNSCC tumors to date are shown below in Figure 6. Mutations in the PTP catalytic domains (PTPRT and PTPRD) and the fibronectin type 3 domain (PTPRD) have been reported to inhibit cellular functions of the phosphatase activity of these proteins. 31,33 PTPRO was recently shown to behave as a tumor suppressor and decrease pSTAT3 in liver cancer. 34 It is noteworthy that activating mutations of upstream mediators of STAT3 in HNSCC including EGFR, JAK, and Src were not detected in our HNSCC cohort. Furthermore, there was no evidence for association of PTPR mutations with HPV status. Published data 32 illustrate that HNSCC tumors bearing PTPR mutations demonstrate higher pSTAT3 expression compared to PTPR wild-type. HNSCC cells transfected with a PTPRT mutation (A1022E or R1040L) demonstrate increased growth relative to EGFP-vector control or wild-type PTPR.

Phase 2 - Ruxolitinib Page 20 of 67

Figure 6. Schematics showing mutations of PTPRT and PTPRD found in HNSCC patient tumors.

[figure not shown]
[figure not shown]

Figure 6. Keys: *Blue*: Meprin/A5/PTPmu domain (MAM); *Green*: Fibronectin type 3 domain (FN3); *Orange*: Protein tyrosine phosphatase catalytic domain (PTPc); *Pink*: immunoglobulin (Ig) or Ig-like domain.

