1.4 Correlative Biomarker Analysis

1.4.1 **Primary Analysis**

Correlative biomarker analysis will be performed on paired pre-treatment specimens (tumor biopsies and blood) and post-treatment samples to determine the modulation of biomarkers by ruxolitinib. Most importantly, biomarkers within the JAK/STAT signaling pathway, including JAK and STAT phosphorylation, PTPR mutation and methylation, inflammatory cytokines and HLA/APM component expression will be assessed to determine their correlation with clinical response to ruxolitinib. Tissue microarrays will be generated from formalin-fixed, paraffinembedded (FFPE) specimens, and these will be used for immunohistochemistry to assess tissue histology, Ki67 labeling, and expression of JAK/STAT pathway proteins, including phosphorylated and non-phosphorylated forms of JAK1, JAK2, STAT1, STAT3, cyclin D1 and Src. PTPR mutations and methylation will be determined by Sanger sequencing/Sequenom³¹ and methylation-specific PCR, respectively. Finally, HLA/APM component expression will be evaluated using IHC or intracellular flow cytometry for TAP1, TAP2, LMP2 and calreticulin, as described³⁵. Remaining specimens after these studies have been completed will be used for additional analysis.

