1.4.2 Additional Analysis

To determine if expression of serum proteins or DNA polymorphisms predict response to ruxolitinib targeting, paired serum (baseline, post-treatment) and baseline peripheral blood mononuclear cells (PBMCs) will be isolated. Blood will be processed for serum and isolation of PBMCs. Serum will be analyzed for proteomic markers using mass spectroscopy and luminex ELISA assays. DNA will be isolated from PBMC samples for SNP analysis. Tissue will be processed for DNA, fluorescence in situ hybridization (FISH), tissue microarrays, and

Phase 2 - Ruxolitinib Page 22 of 67

immunohistochemistry microarrays. Both uniplex and multiplex serum cytokine profile analysis, for correlation with other biomarkers and clinical responsiveness will be performed. For specific cytokines of interest, including IL-6, ELISA kits will be used. For multiplex analysis, the technology developed by Luminex Corporation (Austin, TX, http://www.luminexcorp.com) will be used. It enables a laboratory to simultaneously measure up to 100 analytes in a single microplate well, using very small sample volumes (less than 50 microliters). Previous studies have shown that a multi-marker panel offering the highest diagnostic power was comprised of 22 biomarkers, including EGF, EGFR, Cyfra 21-1, AFP, IL-8, MMP-3, CA 72-4, CA 15-3, MMP-2, TNF-RI, IL-7, HCGb, MIF, Mesothelin, MCP-1, IL-1Ra, FGFb, CEA, sVCAM-1, tPAI 1, RANTES, IGFBP-1. Statistical analysis using our novel ADE algorithm resulted in a sensitivity of 84.5%, specificity of 98%, and 92% of patients with active head and neck cancer correctly classified from a cross-validation serum set³⁶. Further proteomic analysis will be performed using IHC microarrays.

2 Objectives of the Study

2.1 **Primary Objective**

To identify baseline and/or pharmacodynamic biomarkers of response to ruxolitinib based upon association with quantitative change in tumor size (ΔTumor size) following 14-21 days of neoadjuvant ruxolitinib in patients with operable HNSCC. We hypothesize that ΔTumor size will correlate with five prioritized, predictive biomarkers which will be designated for specialized alpha spending: 1) baseline expression of pSTAT3; 2) change in expression of pSTAT3; 3) change in expression of the STAT3 target gene cyclin D1; 4) baseline silencing of protein tyrosine phosphatase receptors D or T (PTPRD or PTPRT) by mutation or methylation; 5) baseline elevation in peripheral inflammatory markers (C-reactive protein [CRP]).

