8.2 Determination of Sample Size and Accrual Rate

8.2.1 Sample Size and Power Estimate

The primary objective of the study is to identify baseline and/or pharmacodynamic biomarkers that might have predictive utility to determine the clinical response to ruxolitinib. As a biomarker study, the statistical design is to accrue a sufficient number of patients and provide 80% power to test one or any of 5 key hypotheses with a shared alpha of 0.15: 1) relationship between clinical response (ΔTumor size) and baseline STAT activation (pSTAT3 expression); 2) relationship between clinical response (ΔTumor size) and change in expression of pSTAT3; 3) relationship between responders (ΔTumor size) and change in expression of cyclin D1: 4) relationship between clinical response (ΔTumor size) and baseline genetic or epigenetic PTPRT or PTPRD silencing; 5) relationship between responders (ΔTumor size) and baseline C-reactive protein. An overall alpha of .15 will be shared equally among the five primary hypotheses. 23 patients with complete biomarker data are needed to achieve 80% power for the 5 primary hypothesis and limit overall family wise error rate (FWER) to 15%. As estimated from our prior window trials, accounting for treatment compliance and quality paired tumor specimens, this will require enrollment of 45 patients. For each biomarker (baseline pSTAT3 expression, change from baseline of pSTAT3 expression, change from baseline of cycline D1 expression, baseline PTPRT or PTPRD silencing and baseline C-reactive protein), mean and standard deviation will be estimated and compared for significance between clinical responders and non-responders of ruxolitinib therapy using Wilcoxon rank tests. Our experience with our phase 0 clinical trial testing the STAT3 decoy also showed correlations between ΔKi-67 (the primary pharmacodynamic efficacy endpoint) and STAT3-target genes falling in the range of .50 to .67. Twenty-five patients will enable a two -tailed Spearman Correlation test at alpha = .03 to detect a true correlation of .56. For the expected 30% of patients with a PTPR mutation, a one-tailed Wilcoxon test will demonstrate increased sensitivity to ruxolitinib via a decrease in tumor size equal to 1.3 standard deviations with 23 patients (8 with a mutation).

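### The power given for primary hypothesis 4 is for PTPR mutation alone, but the hypothesis tested is PTPRT/PTPRD silencing by mutation or methylation, and the number of tails is not settled

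*Combined protocol and SAP*

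**What the plan says.** Section 8.2.1 shares an overall alpha of .15 equally among five hypotheses and states that "23 patients with complete biomarker data are needed to achieve 80% power for the 5 primary hypothesis". The fourth hypothesis in that section concerns "baseline genetic or epigenetic PTPRT or PTPRD silencing". Section 2.1 defines it in the same way, as "baseline silencing of protein tyrosine phosphatase receptors D or T (PTPRD or PTPRT) by mutation or methylation", and section 8.4.2(4) plans a Spearman correlation of that combined variable with percent change in tumor size as the primary analysis.

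The only PTPR-specific power sentence, at the end of section 8.2.1, is about mutation: "For the expected 30% of patients with a PTPR mutation, a one-tailed Wilcoxon test will demonstrate increased sensitivity to ruxolitinib". It assumes a difference of 1.3 SD and 8 mutated patients out of 23. It repeats neither the power nor the alpha. The sentence just before it describes a two-tailed Spearman test at alpha .03 with 25 patients and a true correlation of .56.

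Section 1.3 supplies the prevalences. The Figure 5 caption says that "PTPRD or PTPRT mutations are found in 30% of HNSCC tumors", and the text reports PTPRT methylation in 60% (166/279) of tumors. Section 1.4.1 plans to measure both: "PTPR mutations and methylation will be determined by Sanger sequencing/Sequenom" and methylation-specific PCR.

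**The concern.** A power figure for a two-group comparison depends on how the patients divide and on the effect in the group of interest. The figure in section 8.2.1 uses a 30% minority defined by mutation. The variable to be tested also counts methylated tumors as silenced, and by the protocol's own 60% those tumors alone would make silencing the majority state. No prevalence, effect size or power is given for the combined variable.

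What is at stake is whether the 80% claim can be checked for one of the five primary hypotheses. The number of tails also matters: at alpha .03, and with 23 patients, it can decide whether the result is called significant. In an open-label study it should be fixed before the data are seen.

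**Working it through.** **Inputs.** Alpha per hypothesis is .15/5 = .03 (8.2.1). N is 23, and the effect is 1.3 SD (8.2.1). Mutation prevalence is 30% (8.2.1; 104/347 in 1.3). PTPRT methylation prevalence is 60% (166/279 = 59.5% in 1.3). The overlap of mutation and methylation is not in the documents.

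**Method.** Wilcoxon rank-sum test with exact critical values at .03 (one-tailed) or .015 per tail (two-tailed); power by simulation with normal data and a 1.3 SD shift. For a yes/no marker and untied tumor changes, Spearman's coefficient is a monotone function of the rank sum, so the same figures apply to the Spearman test in 8.4.2(4).

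**Step 1: reproduce the plan.** With 8 vs 15, one-tailed, power is 0.80. The stated calculation is right for mutation with 8 patients. Two-tailed, it is 0.70.

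**Step 2: the count.** 0.30 x 23 = 6.9, about 7; 8/23 = 34.8%. With 7 vs 16, power is 0.77 one-tailed and 0.66 two-tailed.

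**Step 3: the combined variable.** There are three assumptions about overlap:
- Full overlap: 60%, and 0.60 x 23 = 13.8, about 14.
- Independence: 1 - (0.70)(0.40) = 0.72, and 0.72 x 23 = 16.6, about 17.
- No overlap: 0.30 + 0.60 = 0.90, and 0.90 x 23 = 20.7, about 21.

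| Silenced / not | Basis | Power at 1.3 SD, one-tailed / two-tailed | SD detectable with 80% power, one-tailed / two-tailed |
|---|---|---|---|
| 14 / 9 | full overlap | 0.81 / 0.72 | 1.28 / 1.42 |
| 17 / 6 | independence | 0.72 / 0.62 | 1.44 / 1.58 |
| 21 / 2 | no overlap | 0.34 / 0.19 | 2.35 / 2.85 |

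One-tailed power stays at about 80% or above while 8 to 15 of 23 are silenced, and is 0.77 at 16. Two-tailed power is below 80% at every split, with a maximum of 0.74 (12 vs 11).

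**Step 4: effect size.** The 1.3 SD is stated only for mutated tumors; the table carries it over to methylated-only tumors. If the effect there were half as large (0.65 SD, an assumption, with 7 patients mutated), one-tailed / two-tailed power would be 0.55 / 0.43 at 14 vs 9 and 0.42 / 0.32 at 17 vs 6.

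**The case against.** **The Spearman sentence may be the power statement for all five tests.** It carries the per-hypothesis alpha and names the primary test. It follows directly on a remark about Ki-67 and STAT3-target genes, however, names 25 patients rather than 23, and does not allow for a two-valued marker. If it does cover hypothesis 4, the intended test is two-tailed, and the one-tailed PTPR sentence contradicts it. The objection therefore sharpens the question of tails and does not remove the mismatch.

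**The 80% may mean power for at least one hypothesis.** Section 8.2.1 also speaks of testing one or any of the five. On that reading, 0.72 for a single hypothesis contradicts nothing. But the same section also says "23 patients with complete biomarker data are needed to achieve 80% power for the 5 primary hypothesis", which claims it for the five.

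**The prevalences are soft.** The text of section 1.3 gives 104/347 for the PTPR gene family, while the Figure 5 caption assigns 30% to PTPRD or PTPRT. Figure 7 counts 37 tumors with a mutation in any of seven PTPR genes against 171 without (37/208, about 18%). No PTPRD methylation rate is given. This stands: the splits above are scenarios, not estimates. It is also a reason to state the assumption openly.

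**Eight may be deliberate.** Section 1.3 also says nearly one-third, and 23/3 = 7.7. This is fair; the count is one patient and 3 points of power.

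**A stronger reading is tempting:** that hypothesis 4 is underpowered. The documents do not support that. With full overlap and one tail, power is 0.81, slightly above the stated design. A shortfall depends on the overlap, the tails or the effect in methylated-only tumors, none of which the plan settles for the silencing test.

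**Conclusion.** The point holds as a mismatch between the variable powered and the variable tested. At 1.3 SD and alpha .03, power for the combined variable runs from 0.81 down to 0.34 one-tailed, and from 0.72 down to 0.19 two-tailed, across the three overlap assumptions. These figures assume yes/no coding, normally distributed tumor change, the documents' 30% and 60%, and the same effect in mutated and methylated-only tumors.

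The tails are a second open item: one for the mutation Wilcoxon test, two in the Spearman statement, and none given where Spearman is applied to silencing. With two tails, no split of 23 reaches 80% at 1.3 SD. The 7-versus-8 count is minor. The plan should be corrected, but nothing here shows that the sample size must change.

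**What to change.** In section 8.2.1, replace the mutation-only sentence with wording such as:

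> Hypothesis 4: PTPRT/PTPRD silencing is coded yes/no (yes = mutation or methylation of either gene). The joint prevalence is not known. With 14, 17 or 21 of 23 silenced (full overlap, independence, no overlap of 30% mutation and 60% methylation), a two-tailed [one-tailed] rank test at alpha .03 has 80% power to detect a difference of about 1.42 [1.28], 1.58 [1.44] or 2.85 [2.35] SD in % change in tumor size, assuming the same effect in mutated and methylated-only tumors.

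Keep one number of tails; two-tailed matches the Spearman statement already in section 8.2.1. State the same coding and tails in section 8.4.2(4). Do not claim 80% power at 1.3 SD for hypothesis 4 unless the chosen split and tails support it.

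Alternatively, if mutation alone is intended, say so in sections 2.1, 8.2.1 and 8.4.2(4), and restate the power for 7 of 23 as 0.77 one-tailed or 0.66 two-tailed.

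Either route costs only wording. Sample size and alpha do not change. The downside is a less favourable stated power for one of the five hypotheses.

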8.2.2 Replacement Policy

Because this is an open label study with limited number of patients, 23 accrued eligible patients with clinical tumor assessments and biomarkers measurements at baseline and the end of study window are required for the study. Additional patients will be enrolled to replace patients without clinical tumor assessments and completed biomarker measurements for both time points at least one of the five biomarkers of interest. However, all patients will be followed and included for safety assessments.

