3.2 Number of Participants

45 patients will be accrued to achieve the target of 23 eligible patients demonstrating treatment compliance, and with quality paired tumor specimens.

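### The replacement rule in 8.2.2 is garbled and, on its ordinary reading, does not guarantee the 23 patients with complete biomarker data that 8.2.1 requires

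*Combined protocol and SAP*

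**What the plan says.** Section 8.2.1 sets the requirement: "23 patients with complete biomarker data are needed to achieve 80% power for the 5 primary hypothesis". The error rate is divided: "An overall alpha of .15 will be shared equally among the five primary hypotheses". Two component calculations follow. One is for correlations: "Twenty-five patients will enable a two -tailed Spearman Correlation test at alpha = .03 to detect a true correlation of .56". The other is a one-sided Wilcoxon test for PTPR mutation, which looks for greater shrinkage in mutated tumors: "via a decrease in tumor size equal to 1.3 standard deviations with 23 patients (8 with a mutation". To reach 23, "this will require enrollment of 45 patients".

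Section 8.2.2 decides who is replaced. Its first sentence asks for 23 eligible patients with tumor assessments and biomarker measurements at baseline and at the end of the window, without saying which biomarkers or how many. Its next sentence replaces patients without tumor assessments and "completed biomarker measurements for both time points at least one of the five biomarkers of interest".

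Two other sections also describe who counts:

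- Section 3.2: "45 patients will be accrued to achieve the target of 23 eligible patients demonstrating treatment compliance, and with quality paired tumor specimens".
- Section 3.5.1 calls a discontinued patient evaluable if screening tissue was obtained, at least 14 days of drug were taken and response was assessed. It asks for no post-treatment tissue and no biomarker result.

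**The concern.** In ordinary English, a patient with one completed biomarker is not without at least one of the five. Read that way, 8.2.2 keeps such a patient and counts him or her toward the 23.

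A concrete case shows the gap. CRP is drawn at screening and again in the five days before surgery (sections 6.1 and 6.3.2.2). A patient with two CRP values and two scans but no usable post-treatment tissue satisfies the rule. That patient contributes nothing to two of the five primary tests in 8.4.2, change in pSTAT3 and change in cyclin D1. Enrolment could therefore close at 23 while those tests run on fewer.

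The time-point wording also fits badly. Baseline pSTAT3, baseline PTPRT/PTPRD silencing and baseline CRP each need one time point only. Requiring both is meaningful only for the two change markers.

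**Working it through.** **The definitions side by side**

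| Section | What a counted patient must have |
|---|---|
| 8.2.1 | complete biomarker data |
| 8.2.2, replacement sentence | tumor assessment, and at least one of five biomarkers at both time points (ordinary reading) |
| 3.2 | eligibility, compliance, quality paired tumor specimens |
| 3.5.1 | screening tissue, 14 days of drug, response assessment |

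Only 8.2.1 asks for complete data.

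**Inputs from 8.2.1.** Family alpha .15 over five tests gives .15/5 = .03 each. The Spearman test is two-sided with ρ = .56 and 25 patients. The PTPR Wilcoxon test is one-sided, 1.3 SD, 23 patients, 8 of them mutated, hence 8 against 15. The one-sided alpha of .03 is taken from the equal split.

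**The plan's own components.** For the correlation, the Fisher z approximation is power = Φ(atanh(ρ)·√(n−3) − z), with atanh(.56) = 0.633 and z(.985) = 2.170.

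- n = 25: Φ(0.633·√22 − 2.170) = Φ(0.798) = 78.8%. This is close to 80%, so the 25-patient statement is reproduced.
- PTPR Wilcoxon, 8 against 15, normal shift of 1.3 SD, simulated: 80.5%. The 23-patient statement is reproduced.
- The combined claim of 80% for the five hypotheses at 23 is not reproduced for the correlations. At n = 23: Φ(0.633·√20 − 2.170) = Φ(0.660) = 74.5%.

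**Patients needed for 80% at ρ = .56.** n = 3 + ((2.170 + 0.842)/0.633)² = 3 + 22.65, so 26. With the variance inflated by 1.06 for ranks, n = 3 + 1.06·22.65 = 27.01, so 28.

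**Effect of falling below 23.** The documents give no missingness per marker, so 20 and 18 are assumed values. They correspond to 3 of 23 (13%) and 5 of 23 (22%) lacking the marker. The simulated range takes .56 first as a Pearson and then as a Spearman correlation, with 40,000 runs.

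| n with the marker | Spearman power, simulated | Fisher z |
|---|---|---|
| 23 | 69–73% | 74.5% |
| 20 | 62–65% | 67.0% |
| 18 | 55–59% | 61.1% |

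Only the fall from the first row is due to the replacement rule. By Fisher z it is 74.5 − 67.0 = 7.5 points at 20, and 74.5 − 61.1 = 13.4 points at 18. The gap between 80% and the first row is there before the rule acts.

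The PTPR Wilcoxon test, at about the same 8:15 share, falls from 80.5% at 23 to 73.4% at 20 and 66.8% at 18.

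**The case against.** The strongest reply is that the 8.2.2 sentence is ungrammatical and may have been meant to replace anyone missing at least one of the five. That would agree with 8.2.1. The sentence before it asks for measurements at both ends of the window, and 3.2 asks for paired tumor specimens, which is what the two change markers need. Baseline tissue is an inclusion criterion (3.3.1), screening CRP is a required laboratory test (6.3.1), and the biomarker analyses on the surgical specimen are mandatory (6.3.2.3). If 3.2 governs, the remaining loss is mainly assay failure on collected pairs.

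Much of this stands. A reader might infer that the rule will leave the tests short of 23. The documents do not support that: the wording allows a stricter reading, and no failure rate per marker is given. What survives is that 8.2.2 is the operative rule for replacement, its ordinary reading is the loose one, and sites could apply it either way.

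It can also be said that 8.2.1 first speaks of 80% power for one or any of the five hypotheses. On that reading, a shortfall in two markers need not breach 80%. This is fair, but the same section then ties 23 patients with complete data to 80% for the five. The power target needs stating once.

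**Conclusion.** The point holds as a failure to guarantee. Section 8.2.2, ordinarily read, lets a patient with one of five biomarkers count toward the 23, asks for a second time point that three markers do not use, and does not agree with 3.2, 3.5.1 or 8.2.1.

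The cost attributable to the rule is about 7 to 8 points of Spearman power if 20 of the 23 have a given marker, and about 13 to 14 points if 18 do. This assumes a true correlation of .56, two-sided alpha .03 and the loose reading. The values of 20 and 18 are illustrative.

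Two further inferences should be avoided. A reader might blame 8.2.2 for the whole distance from 80%, but at 23 patients with no data missing the correlations already have only about 69–75%. A reader might also expect a corrected rule to restore 80% for all five tests. It would not: the plan's own Spearman statement uses 25 patients, about 26 to 28 are needed, and of the plan's two component calculations only the one-tailed PTPR Wilcoxon reaches about 80% at 23.

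**What to change.** 1. Reword 8.2.2: within the planned 45, replace any patient who lacks the tumor assessment or any one of the five prioritized biomarkers at its required time point(s). That means baseline for pSTAT3, PTPRT/PTPRD silencing and CRP, and both time points for change in pSTAT3 and change in cyclin D1.
2. Use the same definition of biomarker-evaluable in 3.2 and 3.5.1.
3. Restate the power in 8.2.1: about 80% at 23 for the one-tailed PTPR Wilcoxon, and about 69–75% at 23 for a Spearman correlation of .56. Reconcile 23 with 25, and say whether the 80% refers to each test or to any of the five.
4. Report n and power for each test in any case, whether or not 23 complete patients are reached within the 45.

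The cost is one reworded sentence in 8.2.2, matching edits in 3.2 and 3.5.1, and a corrected power statement in 8.2.1. Planned enrolment stays at 45. The stricter rule may use more of the 45 before 23 complete patients are found; since 23/45 = 51%, the plan already allows for nearly half being non-evaluable.
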